5.1.3.2 Behavioral determinant outcomes

Behavioral determinant outcomes are defined as the coaches change in aggregated behavioral determinant scores from baseline to mid-season and from baseline to end-of season.

The aggregated scores include the determinants 1) risk perception, 2) intention, 3) outcome expectancies, 4) action self-efficacy, 5) maintenance self-efficacy, 6) coping self-efficacy, 7) recovery self-efficacy, 8) action plans 9) coping plans and 8) club social support at baseline, mid-season and at end of season. Behavioral determinants will be measured with the *Sports*

STATISTICAL ANALYSIS PLAN for Effectiveness of the Injury-preventive Program #Utviklingsklar

Injury Preventive Behavior Questionnaire containing 56 items with three to six items within each determinant, all assessed using a 7-point Likert scale. The 7-point Likert responses will be transformed into aggregate scores by summing the items related to each determinant and dividing this total by the maximum possible score, resulting in values ranging from 0.14 to 1.0.

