5.2.1 Primary Outcome

Analysis

The primary outcome (weekly injury severity score) will be analyzed with a linear mixed model. The model will include fixed effects for intervention (intervention vs control), time point, intervention x time point interaction, and geographical region (stratification factor in the randomisation). Time point is defined as 1 for the first response to the OSTRC questionnaire (week 42, 2024), 2 for the second response to the questionnaire (week 44, 2024), and so on until 13 for the last response (week 14, 2025). The model will include random intercepts for players nested within clubs. The predicted margins over all time points will be presented for intervention and control separately with 95% confidence intervals (CIs). The effect measure will be the difference between the weekly injury severity score for intervention and control, estimated as the predicted marginal effect of intervention over all time points, based on the fitted linear mixed model. The effect estimate will be presented with a 95% CI and a P-value for the null hypothesis of a difference equal to zero.

The predicted margins for intervention and control will be presented with 95% CIs for each time point in a plot. The estimated intervention effect (difference between intervention and control) with a 95% CI for each time point will also be shown in a plot.

Assumption checks

The distribution of the primary outcome (injury severity score) will be assessed with descriptive statistics and histograms. With a sample size of approximately 2000, the linear mixed model will be robust to quite large deviations from the normal distribution, and the injury severity score is bounded below at 0 and above at 100, so its distribution cannot be severely skewed. Still, in the unlikely case that the distribution of the outcome is deemed to deviate too much from the normal distribution, a log transformation of the outcome will be done prior to fitting the linear mixed model. In that case, an analysis of the untransformed data will be performed as an additional sensitivity analysis. After fitting the model (original scale or log transformed), plots of observed and model-fitted values (by intervention group and time point) will be compared to assess the fit of the model.

Missing data

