5.2.4 Continuous Secondary Outcomes Measured at Three Time Points

Analysis

Two secondary outcomes on coach behavioural determinants are measured at three time points (baseline, mid-season, and end of season): change in aggregated behavioral determinant scores from baseline to mid-season and change in aggregated behavioral determinant scores from baseline to end of season. A linear mixed model will be fitted to the data from all three time points. The model will include fixed effects for intervention (intervention vs control), time point, intervention x time point interaction, and geographical region (stratification factor in the randomisation). The model will include random intercepts for coaches nested within clubs. The predicted margins over all time points will be presented for intervention and control separately with 95% confidence intervals (CIs). The effect measures will be the differences between the changes in aggregated behavioral determinant scores from baseline to mid-season and from baseline to end of season for intervention vs. control. The effect estimate will be based on the predicted margins from the fitted linear mixed model.

Assumption checks

The distribution of the aggregated behavioral determinant score will be assessed with descriptive statistics and histograms. The aggregated behavioral determinant score is bounded below at 0.14 and above at 1.0, so its distribution cannot be severely skewed. Still, in the case that the distribution of the outcome is deemed to deviate too much from the normal distribution, a log transformation of the outcome will be done prior to fitting the linear mixed model. After fitting the model (original scale or log transformed), plots of observed and model-fitted values (by intervention group and time point) will be compared to assess the fit of the model.

Missing data

The linear mixed model will handle missing data in one or two time points per coach under the assumption of missing at random. For some coaches, we may have missing data for all three time points. Because we expect this to apply to very few coaches, they will be excluded from the analysis.

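### Section 5.2.4: bounds do not rule out skew, and the log fallback ignores the direction of skew and replaces the stated effect measure without restating it

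*SAP*

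**What the plan says.** Section 5.1.3.2 describes a questionnaire "containing 56 items with three to six items within each determinant". The items are "all assessed using a 7-point Likert scale". Each determinant score is formed by "summing the items related to each determinant and dividing this total by the maximum possible score, resulting in values ranging from 0.14 to 1.0".

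Section 5.2.4 fits a linear mixed model to baseline, mid-season and end-of-season scores. It defines the target on the score scale: "The effect measures will be the differences between the changes in aggregated behavioral determinant scores from baseline to mid-season". The same contrast is defined for the change up to the end of the season.

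The assumption check in 5.2.4 makes two statements:

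- The score is "bounded below at 0.14 and above at 1.0, so its distribution cannot be severely skewed".
- Nevertheless, a fallback is provided "in the case that the distribution of the outcome is deemed to deviate too much from the normal distribution". The step it then prescribes is that "a log transformation of the outcome will be done prior to fitting the linear mixed model".

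The section gives no criterion for the trigger, no direction of skew, no back-transformation and no restated effect. The football plan repeats these statements and applies them to ten determinants.

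Two neighbouring sections handle the same situation more completely. If the primary outcome is logged, 5.2.1 adds that "an analysis of the untransformed data will be performed as an additional sensitivity analysis". Section 5.2.3 (injury burden) moves to median regression and says that medians and their differences will then be reported.

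**The concern.** There are three separate defects.

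1. The reason given for not expecting skew is wrong. Finite bounds do not keep skewness small.
2. The log is concave: it stretches low values and compresses high ones. It can correct a right tail but lengthens a left one. Scores crowded near 1.0 have a left tail, yet the rule prescribes the log for either direction.
3. A difference between changes in log score is the log of a ratio of ratios. It is not the difference between changes that the section defines as the effect.

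If the rule were triggered and followed as written, the pre-specified effect would not be reported at all for that determinant. If it were triggered for some of the ten football determinants only, their results would appear on two different scales.

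**Working it through.** **Step 1. The plan's own range.** With k items scored 1 to 7 (k = 3 to 6), the minimum is k × 1/(7k) = 1/7 = 0.143 and the maximum is k × 7/(7k) = 1.0. The stated bounds of 0.14 and 1.0 are reproduced.

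**Step 2. Do those bounds limit skewness?** Put a share p of coaches at 1.0 and 1 - p at the floor. Skewness is then (1 - 2p)/√(p(1 - p)).

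- p = 0.90: -0.8/0.3 = -2.7
- p = 0.95: -0.9/0.218 = -4.1
- p = 119/120 (one coach of the roughly 120 named in 5.2.5): -10.8

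These cases are extreme on purpose. They show only that the bounds exclude nothing. They say nothing about the log, because a two-point distribution has the same skewness on either scale.

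**Step 3. What does the log do?** The documents give no score distribution, so this step rests on assumed scenarios: correlated 7-point items, latent SD 1.5, inter-item correlation 0.6, 3 or 6 items per score (5 in the two floor scenarios), 300,000 draws.

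| Mean score | Skewness, raw | Skewness, after log |
|---|---|---|
| 0.23 (floor) | +1.5 | +0.8 |
| 0.32 (floor) | +0.8 | 0.0 |
| 0.57 (symmetric) | 0.0 | about -0.9 |
| 0.71 | -0.3 | -1.1 |
| 0.83 | -0.8 | -1.4 |
| 0.88 | -1.1 | -1.7 |
| 0.92 | -1.5 | about -2.05 |
| 0.97 | -2.8 | -3.3 |

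A second set of assumptions (coach SD 1.0, item SD 0.8, latent item means 5.5 to 6.5) gives the same direction: raw -0.4 to -1.1 becomes -1.0 to -1.5. The log helps in the floor scenarios and makes every ceiling scenario worse.

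**Step 4. What happens to the effect measure?** Equal gains on the raw scale are unequal on the log scale. A gain of 0.10 from 0.50 is a ratio of 0.60/0.50 = 1.20; from 0.80 it is 0.90/0.80 = 1.125. With baselines set far apart to make the point, even the sign can differ:

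- Intervention 0.80 to 0.90, control 0.50 to 0.59.
- Raw: 0.10 - 0.09 = +0.01.
- Log: ln(0.90/0.80) - ln(0.59/0.50) = 0.118 - 0.166 = -0.048, a ratio of 1.125/1.18 = 0.953.

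**Step 5. Is the defined effect kept anywhere?**

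| Section | Fallback | Effect restated? | Untransformed analysis kept? |
|---|---|---|---|
| 5.2.1 | Log | No | Yes, as sensitivity analysis |
| 5.2.3 | Median regression, bootstrap intervals | Yes, medians | Not applicable |
| 5.2.4 | Log | No | No |

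**The case against.** A reader might infer that the fallback rests on the false sentence. It does not. The plan introduces the fallback as applying in spite of that sentence, so deleting the sentence alone changes no step of the analysis.

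A reader might also infer that the log will move the analysis to a worse-fitting scale whenever it is used. The documents do not support that. They do not say where the scores lie, and with floor skew the log would help. The background section reports that coaches needed more knowledge and self-efficacy, which does not establish floor skew but gives no support for a general ceiling.

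Further points deserve weight:

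- Raw skewness of -0.4 to -1.1 is mild to moderate and might never be judged excessive.
- The effect is a within-coach change, so the residuals matter more than the marginal scores. Adding three occasions per coach to the second set of assumptions (occasion SD 0.5, also assumed) gives within-coach residual skewness of about -0.1 to -0.2 raw and -0.24 to -0.35 after the log. The log is still worse, but by little.
- Section 5.2.4 requires observed-versus-fitted plots on whichever scale is used. Misfit could be seen there, although no action is attached to it.
- With a minimum of 0.14 the log can at least be computed. That is not so for permitted values in 5.2.1 (0) and 5.2.5 (-6 to 0), where a log is also the fallback.
- Section 2.4.1 treats all analyses other than the primary as supportive.

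These points limit the severity. They do not answer the incorrect statement, the missing direction in the rule, or the unrestated effect. Tolerance of moderate skew is itself an argument for staying on the raw scale.

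**Conclusion.** The point holds in three parts. The boundedness statement is wrong, and this needs no assumption. The loss of the defined effect under the log, with neither a restated measure nor an untransformed analysis, also needs no assumption about the distribution; it follows once the rule is triggered. The harm from the log's direction is conditional: it increases left skew (by about 0.5 to 0.8 in the assumed ceiling scenarios) and can reduce right skew, and the documents do not say which will arise.

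Severity is modest. The outcomes are secondary and supportive, the trigger is conditional, and the primary analysis and decision rule are untouched. The change is still worth making, because the behavioural determinants are a full secondary objective and the gap can be closed before the data are seen.

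**What to change.** In 5.2.4 of both SAPs:

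1. Delete the statement that the bounds exclude severe skew.
2. Make the untransformed 0.14-1.0 score the main analysis whatever its distribution, so that the stated difference between changes is always reported.
3. Assess the residuals, as 5.2.3 and 5.2.5 do, rather than the raw outcome. If they are clearly non-normal, base the confidence intervals on club-clustered standard errors or on a bootstrap that resamples clubs. The judgement then affects only the interval, not the scale of the effect. Clustered standard errors and bootstrap intervals already appear in 5.2.3.
4. If any log analysis is kept, label it a sensitivity analysis and state its effect as a ratio: the intervention-to-control ratio of relative changes in geometric mean score.

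The cost is an edit to the SAP wording and slightly more analysis work. No data collection changes.

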5.2.5 Ordinal Secondary Outcomes

Analysis

STATISTICAL ANALYSIS PLAN for Effectiveness of the Injury-preventive Program #Utviklingsklar

The ordinal secondary outcomes on coach practices are measured as the change in an ordinal 7-point scale from baseline to end of season. The change (baseline minus end of season) will be an outcome ranging from -6 (score 1 at baseline and 7 at end of season) to 6 (score 7 at baseline and 1 at end of season). This outcome is an ordinal outcome with 13 categories. With approximately 120 coaches, many of the categories will be sparsely populated, and we believe that an ordinal regression model would be a poor choice with these many categories and so few data. Instead, we will compare the mean number of categories of change from baseline to end of season for intervention vs. control. The outcomes will be analyzed with linear regression models with intervention (intervention vs control) and geographical region (stratification factor in the randomisation) as the explanatory variables. The standard errors will be adjusted to account for clustering within clubs. Based on the fitted model, the predicted margins for intervention and control separately and the predicted marginal effect of intervention will be presented with 95% CIs. The observed counts (and percentages) on the original 13-point ordinal scale will be presented for intervention and control.

Assumption checks

The distributions of the residuals from the fitted linear regression models will be assessed with descriptive statistics and histograms. With only 13 possible outcomes, it is very unlikely that the distribution of the residuals will exhibit any signs of large deviations from the normal distributions. Still, in the case that the distribution of the outcome is deemed to deviate too much from the normal distribution, a log transformation of the outcome will be done prior to fitting the model.

Missing data

The main analysis of the ordinal secondary outcomes will be performed on the complete case sample. As a sensitivity analysis, we will impute missing data with multiple imputation. The imputation model will be multinomial logistic regression, stratified by intervention/control, and it will include the following explanatory variables:

- Age level (team)
- Sex (team)
- Education in injury diagnosis/treatment/prevention (coach)
- Access to health personnel (team)
- Coaching experience (coach)
- University-level coaching education (coach)
- Completed coaching courses (coach)
- Satisfaction with injury prevention knowledge in coaching courses (coach)
- Education in health-related field (coach)
- Injury prevention plan (club)
- Participation in injury prevention (Skadefri) club event the last two years (club)
- Employed by club in full-time position (coach)
- Receiving salary for coaching (coach)
- Possessing multiple club roles (coach)
- Number of full-time leaders (club)

STATISTICAL ANALYSIS PLAN for Effectiveness of the Injury-preventive Program #Utviklingsklar

- Member fee (club)
- Age (coach)
- Gender (coach)
- Club
- Region

The number of imputations will equal the percentage of missing values, i.e. 20 imputations for 20% missing data, as per the rule of thumb in (22). In case the imputation model fails to converge, the model will be reduced by one explanatory variable at a time, starting with the last variable listed above and continuing in opposite order as listed.

6. Statistical Software

All statistical analyses will be done in Stata version 17 (StataCorp LLC, College Station, TX, USA).

STATISTICAL ANALYSIS PLAN for Effectiveness of the Injury-preventive Program #Utviklingsklar

7. References

4. Bakken A. Idrettens posisjon i ungdomstida. Hvem deltar og hvem slutter i ungdomsidretten? Oslo: OsloMet - storbyuniversitetet; 2019.
6. Wik EH. Growth, maturation and injuries in high-level youth football (soccer): A mini review. *Frontiers in Sports and Active Living.* 2022;4.

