5.1.3.4 Injury-preventive coaching practices outcomes

The injury-preventive coaching practice outcomes consist of:

1. The change in the extent to which teams complete warm-up as described in the intervention from baseline to end-of season.
2. The change in the extent to which teams complete strength training as described in the intervention from baseline to end-of season.
3. The change in the extent to which players with pain or injuries receive guidance on medical care from baseline to end-of season.
4. The change in the extent to which training and match participation is facilitated for players with pain or injuries from baseline to end-of season.

Coaches will report injury-preventive coaching practices in a study-specific 7-point Likert scale questionnaire at baseline and at end of season. The endpoint will be the change measured on a 7-point scale, which is then converted into a 13-point scale ranging from -6 to +6.

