5.2.5 Ordinal Secondary Outcomes

Analysis

The ordinal secondary outcomes on coach practices are measured as the change in an ordinal 7-point scale from baseline to end of season. The change (baseline minus end of season) will be an outcome ranging from -6 (score 1 at baseline and 7 at end of season) to 6 (score 7 at baseline and 1 at end of season). This outcome is an ordinal outcome with 13 categories. With approximately 120 coaches, many of the categories will be sparsely populated, and we believe that an ordinal regression model would be a poor choice with these many categories and so few data. Instead, we will compare the mean number of categories of change from baseline to end of season for intervention vs. control. The outcomes will be analyzed with linear regression models with intervention (intervention vs control) and geographical region (stratification factor in the randomisation) as the explanatory variables. The standard errors will be adjusted to account for clustering within clubs. Based on the fitted model, the predicted margins for intervention and control separately and the predicted marginal effect of intervention will be presented with 95% CIs. The observed counts (and percentages) on the original 13-point ordinal scale will be presented for intervention and control.

Assumption checks

The distributions of the residuals from the fitted linear regression models will be assessed with descriptive statistics and histograms. With only 13 possible outcomes, it is very unlikely that the distribution of the residuals will exhibit any signs of large deviations from the normal distributions. Still, in the case that the distribution of the outcome is deemed to deviate too much from the normal distribution, a log transformation of the outcome will be done prior to fitting the model.

Missing data

The main analysis of the ordinal secondary outcomes will be performed on the complete case sample. As a sensitivity analysis, we will impute missing data with multiple imputation. The

STATISTICAL ANALYSIS PLAN for Effectiveness of the Injury-preventive Program #Utviklingsklar

imputation model will be multinomial logistic regression, stratified by intervention/control, and it will include the following explanatory variables:

- Age level (team)
- Sex (team)
- Education in injury diagnosis/treatment/prevention (coach)
- Access to health personnel (team)
- Coaching experience (coach)
- University-level coaching education (coach)

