- Completed coaching courses (coach)
- Satisfaction with injury prevention knowledge in coaching courses (coach)
- Education in health-related field (coach)
- Injury prevention plan (club)
- Participation in injury prevention (Skadefri) club event the last two years (club)
- Employed by club in full-time position (coach)
- Receiving salary for coaching (coach)
- Possessing multiple club roles (coach)
- Number of full-time leaders (club)
- Member fee (club)
- Age (coach)
- Gender (coach)
- Club
- Region

The number of imputations will equal the percentage of missing values, i.e. 20 imputations for 20% missing data, as per the rule of thumb in (22). In case the imputation model fails to converge, the model will be reduced by one explanatory variable at a time, starting with the last variable listed above and continuing in opposite order as listed.

6. Statistical Software

All statistical analyses will be done in Stata version 17 (StataCorp LLC, College Station, TX, USA).

STATISTICAL ANALYSIS PLAN for Effectiveness of the Injury-preventive Program #Utviklingsklar

7. References

4. Bakken A. Idrettens posisjon i ungdomstida. Hvem deltar og hvem slutter i ungdomsidretten? Oslo: OsloMet - storbyuniversitetet; 2019.
6. Wik EH. Growth, maturation and injuries in high-level youth football (soccer): A mini review. *Frontiers in Sports and Active Living.* 2022;4.

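### Coach-practice outcomes: the imputation model is too large for about 60 coaches per arm, leaves out the baseline score and gives up region and club first; the main regression does not adjust for baseline

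*SAP*

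**What the plan says.** Both plans define four coach-practice outcomes as changes between two ratings, given "in a study-specific 7-point Likert scale questionnaire at baseline and at end of season" (section 5.1.3.4). Section 5.2.5 takes baseline minus end of season, from -6 to 6, and notes: "This outcome is an ordinal outcome with 13 categories".

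On the main analysis, section 5.2.5 reasons: "With approximately 120 coaches, many of the categories will be sparsely populated, and we believe that an ordinal regression model would be a poor choice". It compares mean change instead, "analyzed with linear regression models with intervention (intervention vs control) and geographical region (stratification factor in the randomisation) as the explanatory variables", with standard errors adjusted for clustering within clubs, on complete cases.

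Multiple imputation is the sensitivity analysis. Its model is described as follows: "The imputation model will be multinomial logistic regression, stratified by intervention/control". Twenty predictors are listed, ending with Club and then Region. On non-convergence, "the model will be reduced by one explanatory variable at a time, starting with the last variable listed above and continuing in opposite order". The football plan repeats both provisions.

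**The concern.** Four things do not fit together.

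- **Size.** An ordinal model is judged too demanding for 13 categories and about 120 coaches. A multinomial model needs a full set of coefficients for every non-reference category, and here it is fitted in each arm separately. The plan's own reason for rejecting the smaller model applies more strongly to the larger one.
- **Drop order.** The fallback removes Region, then Club. Once both are gone, the imputation model lacks a covariate of the analysis model (the stratification factor) and the randomised unit on which the standard errors are based, while auxiliaries such as member fee remain.
- **Missing predictor.** The baseline practice score is collected, is a component of the outcome, and is known for any coach who missed only the end-of-season form. It is not among the 20 predictors.
- **Main model.** The complete-case regression has only intervention and region as covariates, so baseline enters by subtraction alone.

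This imputation is the only missing-data check planned for these four outcomes. A check that cannot be fitted as written, or that ignores the most relevant known variable, gives little assurance about the complete-case result.

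**Working it through.** **Inputs from the SAP.** 7-point scale at both times; about 120 coaches (5.2.5); 1:1 allocation (2.2); 15 clubs per arm to recruit, 13 needed (2.3); 20 imputation predictors, of which four besides Club and Region describe the club: injury prevention plan, Skadefri event, full-time leaders, member fee (5.2.5).

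**The plan's figures.** Differences of two scores from 1 to 7 run from -6 to 6, which is 13 values. 30 clubs × 4 coaches = 120, so about 60 per arm. Both agree with the text.

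**1. The model that was rejected.** Ordinal regression on intervention and region: 12 cut-points + 1 + (regions - 1). With 2 to 5 regions (assumed), 14 to 17 parameters for 120 coaches.

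**2. The imputation model.** Coefficients per arm = (K - 1) × (1 + p), for K populated categories and p predictors at one degree of freedom each:

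| Model | K = 13 | K = 7 | K = 5 |
|---|---|---|---|
| All 20 predictors | 12 × 21 = 252 | 6 × 21 = 126 | 4 × 21 = 84 |
| Region and Club dropped (18) | 12 × 19 = 228 | 6 × 19 = 114 | 4 × 19 = 76 |

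The SAP does not say whether the change or the end score is imputed. K = 7 covers the 7-point end score and also a change score with only seven values in use.

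One degree of freedom flatters Club. With dummies for 13 to 15 clubs, and without Region and the four club-level variables (all fixed by club), 14 other predictors remain: 12 × (1 + 14 + 12) = 324 to 12 × (1 + 14 + 14) = 348.

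Not all 13 categories will be in use. A simulation assumed 30 clubs of 4 coaches, scores rounded and clipped to 1-7, SD 1.5, three regions, and club ICC 0, 0.05 and 0.15. It gave on average 8.6, 7.6 and 6.3 populated change categories per arm at baseline-to-end correlation rho = 0.3, 0.5 and 0.7. That is 7.6 × 21 ≈ 160, 6.6 × 21 ≈ 139 and 5.3 × 21 ≈ 111 coefficients.

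In a further simulation with 50 observed coaches per arm and rho from 0.3 to 0.7, at least one outcome category was perfectly separated in every run, with 20 or 18 predictors, for the change and the end score alike.

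**3. The fallback.** Even one coefficient per coach, a lenient limit, allows p = 60/12 - 1 = 4 predictors at K = 13, or 60/6 - 1 = 9 at K = 7. Working up from the end of the list, 16 or 11 predictors must go. Region and Club are the first two. The four club-level variables stand 10th, 11th, 15th and 16th, so they go as well.

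Dropping Region alone loses nothing while Club is in as dummies: a rank check with 15 clubs gave rank 15 for Club alone and for Club plus Region plus the four club-level variables.

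**4. What baseline carries.** With equal variances at both times:

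- Share of change-score variance explained by baseline = (1 - rho)/2 = 35%, 25%, 15% at rho = 0.3, 0.5, 0.7.
- Variance of the baseline-adjusted relative to the change-score effect estimate = (1 - rho²)/(2(1 - rho)) = (1 + rho)/2 = 0.65, 0.75, 0.85.

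The simulation with clubs and the bounded scale (4000 runs per setting) gave 0.63-0.65, 0.71-0.75 and 0.84-0.85.

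**5. Illustration of bias.** 120 coaches, 30 clubs, about 20% missing end scores, with missingness depending on baseline differently by arm (assumed):

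| rho | Full data | Complete-case change | Imputed, no baseline | Imputed, with baseline | Complete case, baseline-adjusted |
|---|---|---|---|---|---|
| 0.3 | -0.475 | -0.312 | -0.309 | -0.477 | -0.481 |
| 0.5 | -0.466 | -0.343 | -0.342 | -0.469 | -0.468 |
| 0.7 | -0.475 | -0.401 | -0.401 | -0.478 | -0.475 |

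Without baseline, imputation repeats the complete-case error. When missingness did not differ by arm, no method was biased. Changes imputed without baseline implied an end score outside 1-7 in 5% to 12% of cases.

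**The case against.** - **The endpoint is defined as a change, and analysing it as such is valid.** This stands as far as bias goes: under randomisation the estimate is unbiased, and the gain from adjustment depends on a correlation that the SAP does not give. It is a point about precision, but the data are already collected and the gain costs nothing.
- **252 is a ceiling.** It is: it needs all 13 categories populated. The lower counts, 111 to 160 under the simulated assumptions and 126 for the end score, are still about twice the number of coaches or more.
- **The drop rule is conditional, and Club is a sensible first thing to shed because it is the largest block.** The rule does apply only on non-convergence. With this many coefficients and separation in every simulated run, that condition should be expected. Losing Club is understandable computationally, but it does not make the model fit, and a smaller model would not need to lose it.
- **Chained equations could let baseline and end scores predict each other.** They could, but the SAP does not describe this. It names a list, and baseline is not on it.
- **The bias figures come from an assumed missingness pattern.** Agreed. They show what the check could miss, not what will happen, and the amount of missing coach data is unknown.
- **These outcomes are supportive.** Agreed, and this limits the weight of the point.

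**Conclusion.** The concern holds. The imputation model conflicts with the plan's own sparsity argument: 126 to 252 coefficients for about 60 coaches per arm at one degree of freedom per predictor, and 114 to 228 after Region and Club are gone. These counts need only the SAP's figures. The drop order removes the stratification factor and the randomised cluster before any auxiliary, and nothing in the text brings the baseline score into the imputation.

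The missing baseline adjustment in the main regression costs precision and does not bias the result under randomisation. The variance ratio of 0.65 to 0.85 rests on an assumed rho of 0.3 to 0.7 and equal variances.

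The scope is four supportive secondary outcomes in each plan. The primary analysis is untouched. The change should be made, but the trial's main conclusion does not depend on it.

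**What to change.** In section 5.2.5 of both plans:

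1. **Main analysis.** Add the baseline practice score as a covariate alongside intervention and region, and keep the club-clustered standard errors.
2. **What is imputed.** State that the missing 7-point end-of-season score is imputed and the change derived from it.
3. **Imputation model.** Replace the multinomial model with predictive mean matching or linear regression, by arm. Even with every listed predictor at one degree of freedom plus baseline, this is 1 + 21 = 22 coefficients per arm; a short, named auxiliary list would reduce it further.
4. **Variables always kept.** Baseline practice score, region and a representation of club: a random intercept or, if that cannot be fitted with about four coaches per club, a named club-level mean such as the mean baseline practice score.
5. **Fallback.** On non-convergence, drop auxiliaries first, in a stated order, and never the variables in item 4.

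The cost is wording in one section of each plan. No new data are needed, and the model is smaller than the one planned.
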